#### **5.4.3. Study Population Rationale**

HAE affects both males and females, although the disease has a greater burden on females, with an increased frequency and severity of HAE attacks in women (Bork, Meng et al. 2006, Lumry, Castaldo et al. 2010). Estrogen appears to worsen the disease, as evidenced by an increased number of attacks reported following onset of puberty and when estrogen-containing therapy is initiated (Bouillet, Longhurst et al. 2008, Caballero, Farkas et al. 2012). Due to the gender distribution of HAE and the influence of hormones on the frequency of attacks, it is considered important to include both males and females in this clinical trial to gain an early assessment of potential safety and PK differences.

Although there is no evidence of fetotoxicity with BCX7353, pregnant women will be excluded from participation. BCX7353 is early in clinical development and the benefit/risk profile has not been characterized in the general HAE population to allow pregnant women to receive BCX7353. Additionally, any female subject who becomes pregnant during the course of the study will be immediately removed from study drug and followed through the end of the pregnancy.

Women of childbearing potential may be enrolled in this trial only if they agree to utilize at least an acceptable effective contraceptive method. The specific types of allowable acceptable effective contraception outlined in Section 8.2.1 are in accordance with the Clinical Trial Facilitation Group (CTFG) *Recommendations Related to Contraception and Pregnancy Testing in Clinical Trials* document.

The allowance of an acceptable effective contraception method in this trial is based on the completion and outcome of nonclinical studies in accordance with the general recommendations of the ICH M3(R2) guideline that “all female reproduction toxicity studies and the standard battery of genotoxicity tests should be completed prior to the inclusion, in any clinical trial, of women of childbearing potential not using highly effective birth control or whose pregnancy status is unknown.” The completed studies for BCX7353 include a standard battery of genotoxicity testing, 13-week repeat dose toxicity studies in two species, embryofetal development studies in two species, and a fertility and early embryonic development study in rats. As described, the results from all studies indicates no risk to the unborn, thus supporting the option for highly effective or acceptable effective methods of contraception to be used during BCX7353 clinical trials.

Based on past and ongoing studies conducted in HAE patients, it is anticipated that female subjects will comprise at least 50% of the patient population in this study.

#### **5.4.3.1. Rationale for Allowance and Restriction of Concomitant Medications for HAE**

While there are approved therapies in the US and EU for prophylaxis against HAE attacks, including C1 INH infused intravenously, consensus recommendations do not exist for either a standard of care for prophylactic treatment or a definition of indications for prophylaxis. A recent guideline published on the management of HAE by the US HAE Association Medical Advisory board suggests that decisions on when to use prophylaxis should be individualized:

*'The decision about when to use long-term prophylactic treatment cannot be made on rigid criteria but should reflect the needs of the individual patient. Decisions regarding which patients should be considered for long-term prophylaxis should take into account attack frequency, attack severity, comorbid conditions, access to emergent treatment, and patient experience and preference.'* (Zuraw, Banerji et al. 2013)

In the current study, all participants must have access to effective, approved treatments for attacks of angioedema as part of their routine medical care. Each subject will continue to use their prescribed acute medication to treat any attacks, under the medical management plan advised by their physician, throughout the study. This is consistent with multiple guidance documents that strongly support the position that all subjects with C1 INH deficiency should have access to medications for treating attacks (Cicardi, Bork et al. 2012, Zuraw, Banerji et al. 2013).

#### **5.4.4. BCX7353 Risk/Benefit Analysis**

##### **5.4.4.1. Risks for Potential Severe Adverse Reactions**

Given that BCX7353 is a small molecule kallikrein inhibitor with a completed Phase 1 single and multiple dose study, there is an acceptably low risk of severe adverse reactions. Potential risks are outlined below.

##### **5.4.4.2. Risks of Potential Adverse Events with BCX7353**

The initial toxicology studies in rats and monkeys suggest that the primary target organs of BCX7353 toxicity were liver (both hepatocyte necrosis and bile duct hyperplasia), kidney, and skeletal muscle, with toxicities also observed in cardiac and smooth muscle, and the lymphoid system. However, with longer duration of dosing (13 weeks) (albeit with a different drug lot than used in the 28-day studies) there were no significant adverse effects noted. In monkeys dosed 20 mg/kg/day for 13 weeks, there were no adverse effects noted. In rats dosed at 20 mg/kg/day for 13 weeks, only bile duct hypertrophy, hyperplasia and vacuolated macrophages in the liver were noted and these were not considered adverse. No clinically significant toxicities in these organs have been noted during the first in human trial. Mild gastrointestinal symptoms, including diarrhea, abdominal pain, and nausea were noted, particularly at higher doses. In addition, delayed hypersensitivity drug rash was reported.

**Liver:** At 20 mg/kg/day of BCX7353 dosed to rats for 13 weeks, bile duct hypertrophy, hyperplasia, and vacuolated macrophages were present in the liver with evidence of PLD in Kupffer cells on EM. There were no hepatic enzyme or biliary lab marker changes and all these effects were reversible as evidenced in the 6-week recovery animals. At 25 mg/kg/day of BCX7353 dosed to rats for 28 days, there was minimal to mild bile duct degeneration/necrosis and inflammation. At higher doses of 75 mg/kg day, there was minimal bile duct hyperplasia,

hepatocyte necrosis, and hepatocellular vacuolation that correlated to increased AST and ALT on clinical chemistry.

At 20 mg/kg/day dosed to monkeys for 13 weeks, ALT levels were mildly increased in both sexes at Week 4 but demonstrated partial resolution at the terminal collection despite continued dosing, lacked correlative microscopic changes in the liver at the terminal necropsy, and were normal at the recovery collection. In the previous study where monkeys were dosed for 28 days there were enlarged hepatocytes with foamy to large cytoplasmic vacuoles and hyperplasia of oval cells at 100 mg/kg/day. Hepatocellular necrosis was noted at 30 mg/kg/day, but only those effects at 100 mg/kg/day were considered adverse. These changes also correlated with increased transaminases on clinical chemistry. In addition, monkeys had mild decreases in albumin and mild increases in globulin levels at 100 mg/kg/day.

Liver enzymes, bilirubin, gamma-glutamyltransferase (GGT) and alkaline phosphatase (ALP) are being followed closely in clinical trials to monitor for any hepatocellular and biliary system changes. There have been no clinically significant abnormalities observed in any of these analytes during the Phase 1 study. In the 50 subjects treated with BCX7353 for 7 to 14 days, the highest ALT (104 IU/L) and AST (48 IU/L) occurred on Day 14 in 1 subject who was in the 350 mg × 14-day cohort. There was no evidence of any clinically significant abnormality in hepatic synthetic function as monitored by prothrombin time, albumin, and total protein levels in blood.

In the ongoing study, two of the first 23 subjects treated in Part 1 (350 mg BCX7353) experienced a treatment-emergent Grade 3 (one subject) or Grade 4 (one subject) lab abnormality in GGT, along with lower Grade increases in AST, ALT and ALP.

After a DMC review of blinded data on December 13, 2016, triggered as per criteria listed in Section 12.2, the DMC recommended the study dosing continue unchanged but that liver enzymes be monitored on a weekly basis while subjects are on study drug. Therefore, the frequency of monitoring of liver function has been changed from every 2 weeks to weekly in this study. This additional safety monitoring was instituted by a memo from the Sponsor to all sites on December 16, 2016, and was formalized in Protocol Amendment 2, (Version 3.0).

**Kidney**: Although there was no evidence for any renal injury in the 13 week studies in either rats or monkeys, in the 28 day studies both rats and monkeys had renal tubular degeneration/regeneration with vacuolated cells, which was adverse at 75 mg/kg/day for rats and 100 mg/kg/day for monkeys. This appeared to correlate to glycosuria. In addition, female monkeys had significant mononuclear infiltration resulting in a 35% increase in kidney weight from controls at 100 mg/kg/day.

In the Phase 1 trial, no clinically significant abnormalities of renal function, as measured by serum creatinine and creatinine clearance ( $CL_{cr}$ ) have been found. Additional measurements to date of renal injury were also performed; serial evaluations of spot urine microalbumin to creatinine ratio, a marker for glomerular injury, and neutrophil gelatinase-associated lipocalin (NGAL), a novel marker for tubular injury, did not demonstrate any evidence of renal injury.

Renal assessments including creatinine,  $CL_{cr}$ , and NGAL will be regularly monitored in this study.

**Skeletal muscle**: Although there was no evidence for any skeletal muscle injury in the 13 week studies in either rats or monkeys, in the 28 day studies both rats and monkeys had degeneration/necrosis and/or regeneration noted in multiple skeletal muscle groups. In the rat, these changes were also noted in cardiac muscle. Both the skeletal and cardiac muscle changes were adverse at 75 mg/kg/day in rats. The skeletal muscle changes were adverse in the monkey at 100 mg/kg/day. The muscle degeneration was suspected to contribute to the elevated AST on serum chemistry.

In the Phase 1 trial neither AST nor creatine phosphokinase (CPK) demonstrated any clinically significant elevations. In addition, no subjects have experienced any AEs of potential muscular injury.

Given the preclinical data, AST and CPK will be regularly monitored in this study.

**Heart**: Although there was no evidence for any cardiac muscle injury in the 13 week studies in either rats or monkeys, in the 28-day study in rats, degeneration/necrosis and/or regeneration were noted in cardiac muscle and were considered adverse at 75 mg/kg/day. At high doses of BCX7353, monkeys did have decreases in blood pressure and heart rate, with corresponding ECG changes consisting of slowing of the heart rate and lengthening of the RR, QT and QTc intervals and QRS duration.

In addition to cardiac muscle changes and physiologic changes in heart rate and blood pressure, it should be noted that in vitro, BCX7353 inhibited the hERG channel inhibition, although the cardiac action potential was not prolonged. Since hERG inhibition has been associated with Torsades de pointes, ECGs will be performed until the effects in humans are better characterized.

There was no evidence of foamy or vacuolated cells in the heart in either the rat or the monkey.

Cardiac monitoring in the Phase 1 study did not demonstrate any arrhythmias or ischemia. Although there were some subjects with a QTcF interval increase between 30 and 60 msec, none of these subjects had an absolute QTcF > 450 msec and all subjects had transient value(s) which returned to <30 msec increase on the same day or the following day.

Troponin T values were normal at all time points in all Phase 1 subjects. One subject in the single-dose 1000 mg group had a transient elevation in Troponin I on Day 2 to 0.06 µg/L (upper limit of normal [ULN] = 0.04 µg/L) that returned to within normal limits on Day 4 and remained < 0.01 µg/L through follow-up. The subject was clinically asymptomatic, had no Troponin T or creatine kinase (CK-MB) elevations, and had no ECG evidence of ischemia.

Six subjects treated with BCX7353 in the Phase 1 study had treatment emergent elevations from baseline of CK-MB, 2 receiving single doses of 100 mg, 2 subjects receiving 250 mg for 7 days, 1 subject receiving 500 mg for 7 days and 1 subject receiving 350 mg for 14 days. In 5 of the 6 subjects this corresponded to elevated CK ranging from 1.3 to 7.6 × ULN. In addition, 3 of these 6 subjects had elevated CK-MB at baseline. None of these subjects had an elevation of Troponin I or Troponin T or any evidence of ischemia or cardiac muscle damage. In all cases this was noted at the follow-up visit after discharge from the Phase 1 unit. In 1 subject receiving 350 mg for 14 days, the CK-MB was elevated to 6.5 µg/L (normal range = 0.0–2.9 µg/L) at the follow-up visit which was not due to an abnormal CK level. This subject had an elevated CK-MB at baseline of 4.0 µg/L, which improved during study drug dosing. All other labs were normal at the follow-up visit. In particular, Troponin I and Troponin T were normal and there was no evidence of cardiac ischemia. It is unclear why the CK-MB was elevated in this subject but cardiac ischemia is unlikely.

This study will exclude subjects with evidence of cardiac disease as indicated by medical history, family history of sudden death or abnormal screening ECG. Monitoring with ECG, troponin and CK-MB will be regularly monitored in this study.

**Lymphoid system:** Although there was no evidence for any lymphoid system abnormalities in the 13 week studies in either rats or monkeys, in the rat 28-day study lymphoid depletion was noted in the thymus and spleen at 75 mg/kg/day. In contrast, the monkeys generally had hyperplastic lymphoid tissue (spleen and lymph nodes) which was not considered adverse.

In the Phase 1 study, no clinically significant changes in any hematologic parameter or lymphoid tissue were noted. No organomegaly and no lymphadenopathy were noted on physical exam. Complete blood counts and general physical examinations will be regularly monitored in this study.

**Presumed Phospholipidosis:** In the 28 day studies in both rats and monkeys, there were foamy macrophages and vacuolated infiltrates found in multiple organs and various tissues, presumed to be signs of PLD. Vacuolated macrophages were noted in the liver, lungs, duodenum, jejunum, ileum, cecum, nonglandular stomach, mandibular lymph node, mesenteric lymph node, spleen,

and ovaries of rats. Vacuolation was present in the choroid plexus, the pituitary gland, the adrenal cortex, pancreas acinar cells and ductal cells of the parotid salivary gland in rats. In monkeys, foamy cells were noted in the liver, lymphoid tissue and small intestines. In most tissues, these infiltrates did not appear to be adverse and there were no clinical or blood chemistry findings that correlated. However, the infiltrates in the intestinal villi, which were not considered adverse in rats, caused significant villous thickening in monkeys at 100 mg/kg/day that appeared to correlate to possible malabsorption, manifested as decreased weight and low body nutrients. Importantly, the PLD was fully or partially reversible in both species. The partial reversibility in monkeys may have been due to the continued presence of BCX7353 in plasma even at Day 50 of the 28-day dosing study.

In the 13-week studies in rats, the liver showed vacuolated macrophages with electron microscopic features consistent with PLD. In the monkey there was no physical correlate as there were no microscopic abnormalities and no foamy macrophages or vacuolated cellular infiltrates. Increased urinary levels of BMP, an investigational biomarker for PLD, were demonstrated in both rats and monkeys dosed with BCX7353 for 13 weeks.

PLD is not adverse in and of itself and there are approved products that cause this phenomenon without any associated toxicity. It currently cannot be directly measured in an effective and noninvasive way and there are no validated biomarkers in humans ([Chatman, Morton et al. 2009](#)). Since PLD is not a toxic manifestation and cannot be easily measured in humans, end organ toxicity is monitored. PLD may manifest by expanding the thickness of intestinal absorption and pulmonary diffusion tissues. This may result in various clinical findings, such as possible decreased nutrient absorption when PLD is present in intestinal villi.

In the Phase 1 trial, there were no events suggesting PLD in either the intestines or lungs. No clinically significant changes in weight or evidence of malabsorption occurred. In addition,  $D_LCO$  was performed as an experimental marker of foamy macrophage deposition in the lung. Except for a single subject in the 125-mg dose group who had a 22% decrease from baseline, no other clinically significant changes were noted from baseline to end of dosing in the multiple-day cohorts. This subject had no signs or symptoms suggestive of a diffusion deficit. In addition, no differences were seen comparing changes in  $D_LCO$  in BCX7353-treated with placebo-treated subjects.

The primary method of ensuring subject safety will be to monitor organ toxicity and subject well-being through adverse event reporting and vital signs including weight. In addition, monitoring with  $D_LCO$  will be employed as an experimental marker to gauge lung foamy macrophages.

**Gastrointestinal symptoms:** Gastrointestinal symptoms, primarily mild, were noted in all cohorts in the Phase 1 study when BCX7353 was given over 7 to 14 days. Symptoms were primarily lower gastrointestinal (diarrhea and flatulence) at 500 mg QD  $\times$  7 days and primarily upper gastrointestinal (abdominal pain, dyspepsia) at 350 mg QD  $\times$  14 days without any pertinent laboratory or physical exam findings. In the Japanese 250 mg  $\times$  7-day cohort, a single subject had abdominal pain. All subjects reporting these events took study drug in a fasting state. Two subjects discontinued, one after a single 500-mg dose of BCX7353 due to diarrhea and abdominal pain, and one after 10 days of 350 mg BCX7353 due to abdominal pain. Neither subject had any clinically significant laboratory abnormalities. PK analyses of both 250 mg doses administered in Part 1 of Study BCX7353-101 demonstrated no impact on drug exposure from

taking BCX7353 with food. Therefore, in order to help mitigate any gastrointestinal effects, particularly upper abdominal effects, BCX7353 should be taken with food.

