### **5.3.3. Study BCX7353-203**

Interim efficacy, safety, PK, PD, and PK/PD results are available for Parts 1 and 2 of this ongoing proof-of-concept Phase 2 study in subjects with HAE. As of the cut-off date of 19 May 2017, 51 subjects with HAE were randomized and had received up to 28 days of treatment with BCX7353 once daily; 18 subjects received BCX7353 350 mg, 6 subjects received BCX7353 250 mg, and 7 subjects received BCX7353 125 mg. In addition, 20 subjects with HAE had received placebo. Part 3 of the study is currently ongoing.

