### **12.5.2. Graded Abnormalities**

Clinical laboratory results will be graded according to criteria specified in the protocol using DMID Adult Toxicity Table (2007), if applicable.

Any graded abnormality that occurs following the initiation of study drug and up to +30 days after the last dose, and represents at least 1-grade increase from the baseline assessment is defined as treatment emergent. The number and percentage of subjects experiencing treatment-emergent graded toxicities will be summarized by treatment group. A laboratory shift table will be provided to show the baseline grade to the maximum post baseline grade. Laboratory values that do not meet the graded laboratory abnormalities are assigned grade 0 in the shift table.

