14.3.5.3	Summary of Laboratory Values by Visit – Urinalysis	Safety
14.3.5.4	Summary of Graded Shift in Laboratory Abnormalities - Hematology	Safety
14.3.5.5	Summary of Graded Shift in Laboratory Abnormalities – Chemistry	Safety
14.3.5.6	Summary of Treatment-Emergent Laboratory Abnormalities	Safety
14.3.5.7	Summary of Treatment-Emergent Grade 3 and 4 Laboratory Abnormalities	Safety
14.3.5.8	Summary of Lab Toxicity Grade Increase from Baseline	Safety
14.3.6.1	Summary of Vital Signs by Visit	Safety
14.3.6.2	Summary of Body Weight by Visit	Safety
14.3.6.3	Summary of QTcF Categorical Findings by Visit	Safety
14.3.6.4	Summary of 12-lead Electrocardiograms Parameters by Visit	Safety
14.3.6.5	Summary of 12-lead Electrocardiograms Assessment by Visit	Safety
14.3.6.6	Summary of Pulmonary Diffusion data by Visit	Safety
14.3.6.7.1	Summary of Fold x ULN for Liver Function Tests	Safety

Tables	Title	Population
14.3.6.7.2	Summary of Fold x ULN for Liver Function Tests –Subjects with Prior Androgen Use	Safety
14.3.6.7.3	Summary of Fold x ULN for Liver Function Tests –Subjects without Prior Androgen Use	Safety
14.3.6.8.1	Summary of Fold x from Baseline for Liver Function Tests	Safety
14.3.6.8.2	Summary of Fold x from Baseline for Liver Function Tests –Subjects with Prior Androgen Use	Safety
14.3.6.8.3	Summary of Fold x from Baseline for Liver Function Tests –Subjects without Prior Androgen Use	Safety
14.3.6.9.1	Summary of Number of Subjects with Elevations in Post Baseline Liver Function Tests	Safety
14.3.6.9.2	Summary of Number of Subjects with Elevations in Post Baseline Liver Function Tests –Subjects with Prior Androgen Use	Safety
14.3.6.9.3	Summary of Number of Subjects with Elevations in Post Baseline Liver Function Tests –Subjects without Prior Androgen Use	Safety

Figures	Title	Population
Study population		
14.1.1	Consort Diagram	All subjects
14.1.2	Time to study drug discontinuation	RS
Efficacy		
All Efficacy Figure will be repeated for the PP population		
Table Numbering: FAS tables will end as .1; PP tables will end as .2		
14.2.1.1	Plot of Estimated Treatment Effect (If data permit, Forest plot to show estimated between treatment difference and 95%CI, for overall and by each subgroup)	FAS
14.2.1.2	Plot of Individual Attack Rate by Treatment –Confirmed Attack	FAS
14.2.1.3	Cumulative Distribution Function of the Confirmed Attack Rate	FAS

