14.2.4.4	Plot of Percent of plasma BCX7353 trough concentrations ( $C_{tau}$ ) above 4x kallikrein inhibition $EC_{50}$ (35.8 ng/mL) and confirmed attack rate	PK
14.2.4.5	Plot of Percent of plasma BCX7353 trough concentrations ( $C_{tau}$ ) above 8x kallikrein inhibition $EC_{50}$ (71.6 ng/mL) and confirmed attack rate	PK
14.2.4.6	Plot of Average Plasma BCX7353 trough concentrations ( $C_{tau}$ ) and confirmed attack rate	PK
14.2.4.7	Plot of Plasma BCX7353 Concentration by Attack Free Status	PK
14.2.4.8	Plot of Selected Plasma BCX7353 PK Parameters by Attack Free Status	PK
14.2.4.9	Plot of Rate of Attack vs. Plasma BCX7353 PK Parameters (one plot for each PK parameter of interest)	PK
14.2.4.10	Plot of Plasma BCX7353 PK Parameters VS HK parameters	PK and Cleaved HK PD
14.2.4.11	Plot of Cleaved HK Concentration by Attack Free Status	Cleaved HK PD
14.2.4.12	Plot of C1INH Concentration by Attack Free Status	C1 INH PD
The PKPD/Efficacy plots will be performed as data permit, additional figures may also be added.		
Safety Figures		
14.3.1.1	Time course of AST in individuals with treatment-emergent AST abnormalities (spaghetti plot, 1 line for each subject and page by treatment,)	Safety
14.3.1.2	Time course of ALT in individuals with treatment-emergent ALT abnormalities	Safety
14.3.1.3	Time course of ALP in individuals with treatment-emergent ALP abnormalities	Safety
14.3.1.4	Time course of GGT in individuals with treatment-emergent GGT abnormalities	Safety
14.3.1.5	Time course of Direct Bilirubin in individuals with treatment-emergent Direct Bilirubin abnormalities	Safety
14.3.1.6	Time course of Total Bilirubin in individuals with treatment-emergent Total Bilirubin abnormalities	Safety

Figures	Title	Population
14.3.1.7	Peak ALT: Placebo versus BCX7353 subjects	Safety

Listings	Title	Population
Study Population		
16.2.1.1	Subject Randomization	Safety
16.2.1.2	End of Study Record	Safety
16.2.2.1	Inclusion/Exclusion Criteria not Met	Safety
16.2.2.2	Protocol Deviations	Safety
16.2.2.3	Subjects for Whom the Treatment Blind Was Broken	Safety
16.2.4.1.1	Demography	Safety
16.2.4.1.2	HAE Demography – HAE History	Safety
16.2.4.2.1	HAE Demography – Past on-Demand Treatments of HAE	Safety
16.2.4.2.2	HAE Demography – Current on-Demand Treatments of HAE	Safety
16.2.4.2.3	HAE Demography – Past Prophylactic Treatments of HAE	Safety
16.2.4.3	Medical History	Safety
16.2.4.4	Prior Medications	Safety

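### Liver testing became weekly partway through Part 1, so the SAP's all-visit maximum-grade, elevation-count and peak-ALT displays compare dose groups with unequal numbers of draws

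*Protocol*

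**What the plan says.** Protocol 5.4.4.2 (Liver) reports that "two of the first 23 subjects treated in Part 1 (350 mg BCX7353) experienced" a Grade 3 or Grade 4 GGT abnormality. After a DMC review, "the frequency of monitoring of liver function has been changed from every 2 weeks to weekly in this study". On timing it says: "This additional safety monitoring was instituted by a memo from the Sponsor to all sites on December 16, 2016". The current schedule (Protocol Table 3, repeated as SAP Table 1) has full chemistry on Days 14, 29 and 44 and a liver panel on Days 7 and 21. The SAP table presents this as the schedule for everyone.

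SAP 12.5 admits all laboratory samples up to 30 days after the last dose and rules out inferential statistics. SAP 12.5.2 counts subjects with treatment-emergent graded toxicities and adds: "A laboratory shift table will be provided to show the baseline grade to the maximum post baseline grade". The SAP's list of outputs includes treatment-emergent laboratory abnormalities (Tables 14.3.5.6 and 14.3.5.7), "Summary of Number of Subjects with Elevations in Post Baseline Liver Function Tests" (Table 14.3.6.9.1, repeated by prior androgen use), and a figure titled "Peak ALT: Placebo versus BCX7353 subjects" (14.3.1.7). Placebo is pooled over all parts for safety (Protocol synopsis). Nothing in the SAP mentions the earlier testing schedule.

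**The concern.** A maximum, or a count of subjects with any abnormality, can only stay the same or rise as draws are added. Here the number of draws is tied to dose. 350 mg was given only in Part 1, where some subjects were on the sparser schedule. 62.5, 125 and 250 mg were given only in Parts 2 and 3, when every subject was tested weekly. Randomization does not protect comparisons that cross parts, and pooled placebo is a mixture of the two schedules.

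Protocol 5.4.1.3 names liver enzyme abnormalities as one of two dose-related safety findings in its dose rationale. If the lower doses are searched more often than placebo and 350 mg, they can appear worse than placebo with no drug effect, and a real gradient from 350 mg downward can appear shallower than it is.

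**Working it through.** The documents give no figure for this effect, so there is none to reproduce.

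**Inputs**
- Arm sizes through Part 2 (Protocol 5.3.3): "18 subjects received BCX7353 350 mg, 6 subjects received BCX7353 250 mg, and 7 subjects received BCX7353 125 mg", plus 20 on placebo; 18 + 6 + 7 + 20 = 51. With 1:1 allocation in Part 1, about 18 placebo subjects come from Part 1 and 2 from Part 2.
- Part 3 as planned (Protocol 7.1): about 20 subjects at 1:3:3:3, that is 2 placebo and 6 on each dose. Final arms: 350 mg 18; placebo 20 + 2 = 22; 250 mg 6 + 6 = 12; 125 mg 7 + 6 = 13; 62.5 mg 6. Part 4 is left out because it is optional and the SAP does not cover it.
- Scheduled post-baseline liver draws: 5 on the current schedule (Days 7, 14, 21, 29, 44). The earlier schedule is taken as 3 (Days 14, 29, 44), inferred from the two-week interval.
- Sparsely sampled subjects, *s*: not stated. The count of 23 must span both arms, since only 18 subjects ever received 350 mg. It is not dated to the memo. I use 23 as an upper-end figure and 16 as a lower one, split evenly between the arms.

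**Step 1. Share of each arm on the sparse schedule, and mean draws = 5 − 2 × share**

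| Arm | *s* = 23 | *s* = 16 |
|---|---|---|
| 350 mg | 11.5/18 = 64%; 3.7 draws | 8/18 = 44%; 4.1 draws |
| Pooled placebo | 11.5/22 = 52%; 4.0 draws | 8/22 = 36%; 4.3 draws |
| 62.5, 125, 250 mg | 0%; 5.0 draws | 0%; 5.0 draws |

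**Step 2. Excess with no drug effect.** If each draw independently has chance *p* of a graded abnormality (assumed), P(any in *k* draws) = 1 − (1 − *p*)^*k*. The lower-dose excess over placebo is the placebo sparse share × [P(5) − P(3)].

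| *p* | P(3) | P(5) | Difference | Excess, *s* = 23 | Excess, *s* = 16 |
|---|---|---|---|---|---|
| 2% | 5.9% | 9.6% | 3.7 | 1.9 points | 1.4 points |
| 5% | 14.3% | 22.6% | 8.4 | 4.4 points | 3.0 points |
| 10% | 27.1% | 41.0% | 13.9 | 7.2 points | 5.0 points |

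At *p* = 5% and *s* = 23 the arms read 17.3% (350 mg), 18.3% (placebo) and 22.6% (lower doses). 350 mg and placebo differ by only 1.0 point. With fully correlated draws within a subject the excess would be zero.

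**Step 3. Detection of a real elevation.** An elevation of *D* days with onset uniform over Days 1 to 28 (a span of 27 days) is caught at visit *v* if onset lies between *v* − *D* and *v*.
- 3 days: earlier schedule (3 + 2)/27 = 19%; current (3 + 3 + 3 + 2)/27 = 41%.
- 7 days: earlier schedule, onset on Days 7–14 or 22–28, (7 + 6)/27 = 48%; current, Days 1–21 or 22–28, (20 + 6)/27 = 96%.
- 10 days: earlier schedule (10 + 9)/27 = 70%; current 100%.
- 14 days: earlier schedule (13 + 13)/27 = 96%; current 100%.
- 21 days: 100% on both.

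Detection relative to the weekly-tested doses is 1 − share × (1 − earlier/current). At 7 days with *s* = 23, this is 1 − 0.64 × 0.50 = 0.68 for 350 mg and 1 − 0.52 × 0.50 = 0.74 for placebo, so 350 mg against placebo is 0.92. With *s* = 16 the figures are 0.78 and 0.82. At 14 days both arms are at 0.98.

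For all active subjects pooled (11.5 of 49 sparse), as the peak-ALT figure's title suggests, detection relative to placebo is 1.20 at 7 days and 1.01 at 14 days, with no true difference.

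**The case against.** The strongest case against is that the effect is small and largely visible in displays already planned.

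- *Exposure.* Subjects still on treatment on 16 December 2016 could have moved to weekly draws, so having been treated by then does not mean sparsely sampled. This stands, and is why 23 is only an upper-end figure.
- *Assumptions.* Liver enzymes in one person are serially correlated, and the per-draw chance is not in the documents. No elevation durations are given for subjects; the only time course described is for monkey ALT, over weeks. This stands, and limits the size.
- *Scale.* 4.4 points on arms of 6, 12 and 13 is about 0.3, 0.5 and 0.6 of a subject. True, but with arms this small one or two subjects shape the reading of a dose.
- *Other displays.* SAP 12.5.1 summarizes values by nominal visit, individual time courses and listings are planned, and nothing is tested. Protocol 13.2.5 describes toxicity shifts by study visit. The by-visit summaries are unaffected. However, the SAP's shift table runs from baseline to the maximum grade, and the subject counts readers will use to compare doses are not by visit.
- *Unscheduled draws.* Confirmatory repeats (Protocol 12.2) also enter the tables and are not in the counts above. This stands.
- *Remedy.* Replacing the main tables with Days 14, 29 and 44 would drop the weekly draws that the DMC asked for. This stands, so the restricted versions should be additions.

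A reader might also infer that the fold-ULN and fold-from-baseline tables (14.3.6.7 and 14.3.6.8) use maxima. Their titles do not say so, and they are left out of this point.

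**Conclusion.** The concern holds as a limitation of specific descriptive displays. As written, the SAP's treatment-emergent counts, maximum-grade shift, elevation counts and peak-ALT figure mix two sampling schedules that line up with dose. The affected contrasts are lower doses versus pooled placebo, 350 mg versus lower doses, and pooled active versus placebo. Without a drug effect, the lower-dose excess over placebo is about 1.4 to 7.2 points, given 16 to 23 sparsely sampled subjects, an even split, planned Part 3 arms and independent draws at 2 to 10%. It is smaller with within-subject correlation. For real elevations the bias matters at about a week or less and is negligible from about two weeks.

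Three stronger readings are not supported:
- *The whole 350 mg and placebo arms were under-sampled.* Only Part 1 subjects treated before the memo are affected, and their number is not stated.
- *350 mg versus placebo is materially biased.* Both were randomized concurrently in Part 1, and relative detection is 0.92 at 7 days and about 1.00 at 14 days.
- *The interim liver signal at 350 mg is an artifact.* Protocol 5.3.3.1 reports transaminase elevations mainly at 350 mg despite the sparser sampling there. The bias would understate that signal; it would not create it.

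**What to change.** Keep the all-visit tables as the main safety displays. In SAP 12.5.2 and the output list, add versions of four liver displays restricted to the scheduled visits common to both schedules (Days 14, 29 and 44), and state that these are used when comparing dose groups:
- the baseline-to-maximum-grade shift
- treatment-emergent liver abnormality counts (14.3.5.6 and 14.3.5.7)
- numbers with elevations (14.3.6.9)
- the peak-ALT figure (14.3.1.7)

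Report the number of liver draws per arm, which also replaces the assumed count of sparsely sampled subjects with the real one. Footnote the 16 December 2016 change on every affected output.

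The restriction gives every arm three scheduled post-baseline draws. The cost is SAP wording, a visit filter and a few extra outputs, with no change to data collection. The downside is that the common-visit versions omit Day 7 and Day 21 peaks, which remain in the all-visit tables and listings.
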